#### 3.2 Outcomes

The **primary outcome** for the study is treatment failure at any point greater than 6 weeks after the participant leaves the operating room; note that per protocol requirements, the patient cannot leave the operating room as a treatment failure. A participant will be considered a treatment failure if any ONE of the following criteria is met:

- 1) Report of bothersome vaginal bulge symptoms (see definition below), or
- 2) Re-treatment for prolapse (surgery or pessary), or
- 3) Any prolapse measure (Ba, C, Bp) is beyond the hymen (i.e. >0 cm)

Bothersome vaginal bulge symptoms = positive response to Question 3 of the PFDI-20: Do you usually have a bulge or something falling out that you can see or feel in your vaginal area? AND any degree of bother.

Participants not considered a treatment failure for the primary outcome will be considered a treatment success.

A number of **secondary outcome measures** will be used to support the analyses for the secondary aims listed earlier. Outcomes that will be used in the planned analyses in the primary ASPIRE manuscript associated with each of the secondary aims include:

- 1. Anatomical measures of treatment efficacy in the two treatment arms obtained at 6-month intervals after surgery:
  - a. Mean and median POPQ point location measures postoperatively in the two treatment arms.
  - b. Proportion of participants in each group with C > -2/3 TVL
  - c. Mean Median values of the maximum extent of prolapse (defined as leading edge of prolapse-Ba, C, Bp)
- 2. Functional measures of treatment efficacy in the two treatment arms as obtained from the measurement at 6 weeks as well as those at 6 months post-surgery and every subsequent 6-month time period through 5 years post surgery:
  - a. Participant impression of overall prolapse improvement at 6-month post-operative intervals as measured by Patients Global Impression of Improvement (PGI-I),
  - b. Mean overall prolapse symptoms at 6-month post-operative intervals based on POPDI-6 scores, and the overall PFDI total score .
  - c. Urinary function measured at 6-month post-operative time points using:
    - i. Mean UDI-6 scores
    - ii. Risk of de novo voiding dysfunction

- iii. Risk of de novo incontinence (stress, urge, and mixed)
- d. Sexual functional measures obtained at 6-month post-operative time points including:
  - i. PISQ-IR scale measures
  - ii. Risk of de novo dyspareunia
- e. Bowel function obtained at 6-month post-operative time points using CRADI-8 scores
- f. Quality of Life (QOL) measures obtained at 6-month post-operative time points including:
  - i. General SF-12 physical component and mental component scales
  - ii. Pelvic QOL as measured by PFIQ total score and three subscales (prolapse: POPIQ, urinary: UIQ, bowel: CRAIQ)
  - iii. Functional activity as measured by the Functional Activity Assessment Scale (FAS)
- g. Regret/Satisfaction:
  - i. Regret with Decision Regret Scale (DRS-PFD)
  - ii. Satisfaction with Decision Scale (SDS-PFD)
- 3. Safety and tolerability of the two treatment regimens:
  - a. Intraoperative safety measured in each of the treatment arms including:
    - i. Mean operative time
    - ii. Estimated blood loss
    - iii. Proportion of participants with blood transfusion
    - iv. Intra- and post-operative complications categorized using a modification of the Dindo Classification.
  - b. Risk of adverse events on the two treatment arms as measured by proportion of participants with any of the following events:
    - i. Mesh related complications: mesh exposure in the vagina or mesh erosion into another organ; note that level of complication will be characterized into based on the following response classification schema: (a) None or nonsurgical medical intervention only; (b) Minor or intra-office surgical intervention; (c) Outpatient surgery; (d) Inpatient surgery
    - Rates of pain captured from the modified Surgical Pain Scale (SPS), pain medication use (during 24 hours prior to completion of the SPS Assessment), and Body Part Pain Scales (BPPS) assessment.
    - iii. Pelvic infection
      - 1. Risk of perioperative infections
      - 2. Risk of urinary tract infections
      - 3. Vaginal infections with flora uncommon to the vaginal canal

- iv. Risk of any of De novo vaginal bleeding, atypical vaginal discharge, fistula formation, neuromuscular problems (including groin and leg pain)
- v. Need for subsequent procedures- Any surgical or non-surgical treatment for pelvic floor disorders (including urinary incontinence, voiding dysfunction, defecatory dysfunction or fecal incontinence, recurrent prolapse, and dyspareunia/pelvic pain).
- vi. Risk of vaginal scarring defined as: De novo vaginal scar requiring medical or surgical intervention, or adversely affecting quality of life.
- vii. Risk of Vaginal shortening, de novo dyspareunia, and
- viii. Risk of worsening dyspareunia with AE survey instrument.

The following study outcomes are to be presented in secondary manuscripts, each with its own SAP. Definitions and analyses for these outcomes are not specified in this SAP, which covers analyses to be presented in the primary results manuscript:

- 4. Key predictors of poor treatment outcomes defined as the effect of advanced prolapse, age, obesity, smoking, estrogens, primary vs. recurrent prolapse on higher risk of treatment failure.
- 5. Body image as measured by the *BIPOP Scale* at 6-month post-operative intervals.
- 6. Cost-effectiveness of the three treatment regimens
  - a. Clinical costs associated with participant's use of medical and non-medical resources related to urologic or gynecologic conditions will be collected during the follow up period. Direct and indirect costs of the treatment of apical pelvic organ prolapse with native tissue surgical repair or transvaginal mesh repair and women's preference for health states for improvement in pelvic organ prolapse will be estimated.
  - b. Preference-based utility index determined from SF-6D.
- 7. Global Composite Outcome
- 8. Patient Perspectives in Adverse Event Reporting (PPAR) Study, which includes patient reporting of frequency and severity levels of selected AEs and complications compared against physician assessments from the same events.
- 9. Frailty ASPIRe Study (FASt), which includes measurements of mini-cog, Katz ADL, functional comorbidity index, Functional Assessment Scale, and timed up and go.

#### 4 STUDY METHODS

[figure not shown]
#### 4.1 Overall Study Design and Plan

The study is a multi-center randomized, surgical trial of women with symptomatic post-hysterectomy apical (cuff) prolapse desiring surgical treatment. This study will compare the three available surgical treatments performed in usual practice. The purpose of this study is to compare two commonly performed mesh apical repairs (sacral colpopexy vs. Apical Transvaginal Mesh) and vaginal native

tissue apical repairs. The primary outcome is measured over time (up to 60 months) using a survival analysis approach.

Participants are followed in ASPIRe until the last participant reaches 36 months of follow-up, so at study completion, participants will have variable follow-up between 36 and 60 months.

A study schematic is shown below:

\*All groups may receive concomitant anterior and/or posterior repairs and full-length mid-urethral slings as indicated, per the discretion of the surgeon.

#### 4.2 Study Population

The study population was planned to be comprised of 363 participants (who were enrolled, consented, randomized and treated) as defined by the following eligibility criteria:

The following paragraph comes from the DSMB Open Report's Protocol Synopsis section and is consistent with the protocol.

Inclusion Criteria:

- 1. Women aged 21 or older
- 2. Prior total hysterectomy (no cervix present)
- 3. Prolapse beyond the hymen (defined as Ba, Bp, or C > 0 cm)
- 4. Vaginal cuff descent into at least the lower two thirds of the vagina (defined as point C> -2/3 TVL)
- 5. Bothersome bulge symptoms as indicated on question 3 of the PFDI-20 form relating to 'sensation of bulging' or 'something falling out'
- 6. Desires surgical treatment for post-hysterectomy vaginal prolapse
- 7. Available for up to 60 month follow-up

Exclusion Criteria:

1. Previous synthetic material or biologic grafts (placed vaginally or abdominally) to augment POP repair including anterior, posterior and/or apical compartments

- 2. Known previous formal SSLS performed for either uterovaginal or posthysterectomy vaginal vault prolapse
- 3. Known adverse reaction to synthetic mesh or biological grafts; these complications include but are not limited to erosion, fistula, or abscess
- 4. Unresolved chronic pelvic pain-active
- 5. Prior abdominal or pelvic radiation
- 6. Contraindication to any of the index surgical procedures
  - a. Known Horseshoe Kidney or Pelvic Mass Overlying the sacrum
  - b. Active diverticular abscess or diverticulitis
  - c. Shortened vaginal length (<6 cm TVL)

#### 4.3 Study Arm Assignment and Randomization

After eligibility is determined and consent is obtained, randomization will occur. Ideally, the time from randomization to surgery will be no longer than 6 weeks (42 days). This time interval will be tracked to determine if delay from randomization to surgery ultimately impacts entry into study represented by those patients undergoing the index surgical procedure. If more than 6 weeks transpires between randomization and surgery, a protocol deviation will be completed. If another visit (i.e. preoperative visit) occurs after randomization, the surgeon should continue to mask the patient to the details of the randomized apical procedure until after completion of the surgery. Randomization in the operating room is not feasible because of the unique equipment to perform laparoscopic and robotic sacral colpopexy. Often robotic rooms are in high demand and need to be reserved and utilized when scheduled.

The randomization will occur in a ratio of 1:1:1 for each treatment arm with an equal chance of being randomized into each treatment group. While the potential existed to perform a 2:2:1 (SC:TVM:NT) randomization scheme given the prior reported evidence using composite outcomes, the working group believes that this scheme would significantly increase patient confusion in counseling for the study and may impact investigator equipoise. In addition, this randomization schema would result in unequal group size, making evaluation of adverse events more difficult and potentially unbalanced between groups.

Randomization will be performed using permuted blocks with a block size that is known only to the DCC and will be stratified by site and age category (<65 and  $\geq$ 65). For each participant, the webbased system will determine the treatment allocation from a static randomization table developed by the study randomization statistician prior to the start of the study. Only the study statistician and randomization system programmer will have access to the randomization table to minimize the risk of selection bias.

On April 16, 2019, the FDA ordered the removal of transvaginal mesh products including Uphold LITE from the market. The PFDN Steering Committee, with approval from NICHD and the DSMB, halted study enrollment for new patients and halted randomization into the TVM arm. At the time, there were 344 completed surgeries and 18 remaining consented or randomized participants who were awaiting surgery. Remaining patients that were randomized to TVM will be re-randomized to receive one of the two remaining arms (SC and NT). This randomization will occur in a ratio of 1:1

Beginning after April 18, 2019, the pending participants who have not undergone surgery will be notified that they will not be randomized into the TVM arm given that this arm is closed at this time. These participants will remain masked to their surgical randomization (SC and NT) until after their surgical repair.

All remaining participants were randomized by the original electronic randomization system. If a participant was randomized to TVM, then they were manually re-randomized to one of the other two treatment arms (SC or NT) in a ratio of 1:1 using a single non-stratified randomization list with permuted blocks of size 2 and 4. The new assignment is communicated to the unmasked site coordinator and updated in the Medidata RAVE Data Management System. This process including Quality Control (QC) procedures was documented in a Note to File dated April 23, 2019.

#### 4.4 Masking and Data Lock

#### **4.4.1** General Masking Procedures

The participant will remain masked until after surgical repair. Those participants receiving sacral colpopexy will have abdominal incisions, making masking for this technique impossible. Because masking is impractical for the sacral colpopexy arm, the unmasking of the two vaginal arms will occur postoperatively. Given that the primary outcome is based primarily on outcome measures obtained by a masked examiner, unmasking of the participants should not bias the outcomes.

The study surgeon is providing clinical care to enrolled participants, thus masking the surgeon to treatment allocation or participant symptoms is not practical or feasible, other than the allocation concealment prior to surgical randomization.

To minimize biases, follow-up POP-Q measures and complications identified via a physical exam will be obtained by co-investigators or study nurses who are masked to the treatment group. Given the masked follow-up, assessment of efficacy outcomes will not occur until the 6-month visit and participants who all have had prior hysterectomy present with abdominal incisions should not risk unmasking. The masked examiner should not inquire about surgical type and the participant should be instructed not to discuss with the masked examiner. Any participant's concerns with details and specifics of the surgery should be forwarded to the participant's surgeon. We realize that unmasking may occur. If masking occurs, the site should complete a protocol deviation.

Masking	Sacral Colpopexy Intervention	Vaginal Mesh Intervention	Native Tissue Intervention
Participant	Preop only	Preop only	Preop only
Study Coordinator or Study Nurse	No	No	No
Telephone Interviewer (if applicable)	No	No	No
Study Surgeon	No	No	No
Anatomic Evaluator	Yes	Yes	Yes

#### 4.4.2 Database Lock

The ASPIRe (Medidata) database will be locked approximately 6 to 8 weeks after the last subject completes her 3-year study visit. The last surgery was performed on June 10, 2019, and that participant's final ASPIRe visit (3 year) is estimated to occur around June 2022. The details of the database lock are outlined in the separate database lock plan.

The E-ASPIRe (REDCap) database is maintained separately from the ASPIRe database and is outside the scope of this SAP.

#### 4.5 Study Flow Chart of Assessments and Evaluations

The study flow chart of visits, assessments and evaluations is in Table 3.

Table 3 Study Flow Chart of Assessments and Evaluations

	TIMELINE OF MEASURES													
MEASURE	SCREE	BAS	PERI	6 WK	6M	12	18	24	30	36	42	48	54	60
	Ν	Е	OP			Μ	Μ	Μ	Μ	Μ	Μ	Μ	Μ	Μ
		LINE												
Demographics	Х													
Medical History	Х													
Physical Exam (height,		Х												
weight and PVR)														
Surgeon's Report and			Х											
Hospitalization														
POP-Q for Inclusion		Х												
Criteria														
Unmasked Staff														
Study Surgery Status			Х											
6 Week Unmasked				Х										
Evaluator Assessment														
(includes Complications														
Assessment)														
6 Week Postoperative				Х										
Recovery Assessment														
6-60 Month Masked					Х	Х	Х	Х	Х	Х	Х	Х	Х	Х
Evaluator Assessment														
(includes POP-Q and														
Complications Assessment)														
Retreatment and					Х	Х	Х	Х	Х	Х	Х	Х	Х	Х
Complications Assessments														
Unmasked														
(6-60 month visit form)														
AE Review			X	X	X	Х	Х	Х	Х	Х	Х	Х	Х	Х
Exams for Mesh Exposure				X	X	Х	X	Х	Х	Х	Х	Х	Х	Х
Non-Pain Med Collection		Х	Х	Х	Х	Х	Х	Х	Х	Х	Х	Х	Х	Х

Version 1.0, 8/17/2022; Page 15

#### Pelvic Floor Disorder

TIMELINE OF MEASURES														
MEASURE	SCREE	BAS	PERI	6 WK	6M	12	18	24	30	36	42	48	54	60
	Ν	Е	OP			Μ	М	Μ	Μ	М	Μ	Μ	М	Μ
		LINE												
Catheterization Follow-Up*					Q 2 we	eks if n	eed for	continuo	ous cath	eterizati	on post	6-Week	Visit	
Functional Activity Scale		Х			Х	Х		Х		Х		Х		Х
Surgical Pain Scale		Х		Х	Х	Х		Х		Х		Х		Х
Body Part Pain Score		Х		Х	Х	Х		Х		Х		Х		Х
PFDI-20 (includes POPDI-	Х				Х	Х		Х		Х		Х		Х
6, CRADI-8, UDI-6)														
PFDI-20 Question 3 Only							Х		Х		Х		Х	
PFIQ-7		Х			Х	Х		Х		Х		Х		Х
PGI-I					Х	Х		Х		Х		Х		Х
PISQ-IR		Х			Х	Х		Х		Х		Х		Х
BIPOP		Х			Х	Х		Х		Х		Х		Х
SF-12		Х			Х	Х		Х		Х		Х		Х
DRS-PFD/SDS-PFD						Х		Х		Х				
*If 6 Week Post-Operative Visit indicates that participant requires continued catheterization, complete this every 2 weeks until catheterization														
ends		1						1						

#### 5 ANALYSIS POPULATIONS

Because randomization occurred prior to scheduling the surgery, some randomized patients did not receive surgery. Also, during surgery some patients were determined by the surgeon to be inappropriate candidates to receive the randomized surgery due to anatomic or other contraindications discovered at the time of the surgery and undeterminable prior to surgery. In these cases, the surgeon selected amongst the other two study surgeries based on physician preference.

Evaluations for superiority will follow a modified intent-to-treat (MITT) approach, and evaluations of non-inferiority will follow a per-protocol approach, which is the customary conservative approach for non-inferiority hypotheses.

To define the MITT population, the intent-to-treat population (all randomized participants) is modified to remove patients who were randomized but never received surgery.

The per-protocol population is the subset of the modified intent-to-treat population excluding all major protocol violations related to study treatment, which might be receipt of a treatment other than the randomized treatment and might be another type of violation.

In addition, given that some patients received a treatment selected by the physician when their randomized treatment was contra-indicated, the MITT and Per-protocol populations were further refined so that treatment switches that were conservative against the null hypothesis are included in the population, and treatment switches that might make the comparison biased against the null are excluded (see below).

Safety data will be evaluated for the safety population that will exclude randomized participants who discontinued the study without having surgery. Participants who received an alternate surgery (treatment switch) after an intraoperative complication or medical contraindication or received a type of surgery other than one of the 3 study treatments will be presented by their randomized (index) surgery. Participants whose treatment was switched prior to surgery or very early during surgery with no initial intraoperative complication caused by the randomized (index) surgery or medical contraindication for the selected surgery (i.e. participant refusal or accidental switch) will be presented by their switched final procedure they received in safety displays. Such participants will be identified by study PI review prior to database lock.

Specifically, populations are defined as follows, supported by the chart (**Table 3**) evaluating the impact of each type of treatment switching on the analysis.

Populations were defined considering all possible types of treatment switching in a blinded fashion without knowing if particular treatment switch scenarios occurred. As such, although all scenarios were considered, planned sensitivity analyses are specified a priori to be conducted only if there are at least 6 participants whose inclusion or values will be impacted by implementing that analysis. Six was selected prior to data unblinding since if a treatment group had 6 such issues, 6 is 5% of the planned 120 participants per treatment arm. In addition, if the MITT-narrow population is identified as only being 2 or fewer patients smaller than the MITT population, then the benefit of applying the MITT-narrow population definition is a priori considered to be outweighed by the benefit of instead using the MITT population in place of the MITT-narrow population in order to achieve results that are substantially easier to present and interpret. After database lock and unblinding, but prior to conducting any efficacy analyses, the population sizes will be evaluated and any such evaluations that

deemed not to be done or to use a different analysis population based on these sample size rules will be documented. Two was selected prior to data unblinding as a very small number unlikely to impact analysis at a level that would warrant the complexities of having a separate analysis population.

**MITT:** all randomized patients, excluding patients who discontinued the study without having surgery. Treatment switchers are included in the treatment to which they were randomized.

[figure not shown]
**MITT- narrow**: all randomized patients, excluding patients who discontinued the study without having surgery and patients randomized to receive SC but received TM or vice-versa (randomized to TM but received SC). This is a subset of MITT. Treatment switchers are included in the treatment to which they were randomized.

**Per Protocol**: all randomized patients excluding all major protocol violations related to treatment including patients who discontinued the study without having surgery, all patients with treatment-related protocol violations, and all patients who did not receive their randomized treatment. This is a subset of the MITT-narrow.

Aim 1 Per Protocol Sensitivity (A1PPS): all randomized patients excluding all major protocol violations related to treatment including patients who discontinued the study without having surgery, all patients with treatment-related protocol violations, and all patients who did not receive their randomized treatment, EXCEPT that TM to NTR switchers are NOT excluded. This is an expansion of the Per-protocol population.

**Safety**: all randomized patients, excluding patients who discontinued the study without having surgery. Treatment switchers are included in the treatment they were randomized or received, based on medical review of the intra-operative condition or event that led to the switch prior to database lock. This is the same participants as the MITT population.

A Venn diagram of the efficacy populations is as follows:

Aim 1 Per-Protocol Sensitivity Pop rand. and treated, excludes all switchers EXECPT TM-to-NTR switchers, and any other major study-treatmentrelated protocol violations

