Because randomization occurred prior to scheduling the surgery, some randomized patients did not receive surgery. Also, during surgery some patients were determined by the surgeon to be inappropriate candidates to receive the randomized surgery due to anatomic or other contraindications discovered at the time of the surgery and undeterminable prior to surgery. In these cases, the surgeon selected amongst the other two study surgeries based on physician preference.

Evaluations for superiority will follow a modified intent-to-treat (MITT) approach, and evaluations of non-inferiority will follow a per-protocol approach, which is the customary conservative approach for non-inferiority hypotheses.

To define the MITT population, the intent-to-treat population is modified to remove patients who were randomized but never received surgery due to patient-specific reasons unrelated to the randomized treatment.

The per-protocol population is the subset of the modified intent-to-treat population excluding all major protocol violations related to study treatment including receipt of a treatment other than the randomized treatment.

Safety data will be evaluated for the safety population that will exclude randomized participants who discontinued the study without having surgery and participants who received a non-study surgery rather than one of the three study surgeries. Treatment switchers will be included in the treatment they received.

M.3. Statistical Data Analysis

Both for the overall global test across cohorts and within each of the three cohorts, surgical failure rates will be compared using survival analysis approaches appropriate for interval censored data (e.g. interval censored piecewise proportional hazards models) and secondary outcomes will be reported as rates in each group or as group means and evaluated

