#### Analysis Populations used for Analysis of the primary outcome (time to treatment failure), including sensitivity analyses

Populations to be used in the analyses for the primary and secondary efficacy outcomes are summarized in Table 2:

Table 2 Summary	of Analysis Populatio	ns
------------------------	-----------------------	----

	Primary Efficacy					
Туре	Aim 1Aim 1aNon-inferiority of TVM to SCSuperiority of TVM to SC		Aim 2 Superiority of TVM to NTR	Aim 3 Superiority of SC to NTR	All Secondary Efficacy Outcomes	
Primary	Per-Protocol	MITT	MITT-narrow	MITT-narrow	MITT	
Sensitivity	Aim 1 PP Sensitivity Pop					
Supportive	MITT	Per-Protocol	MITT and Per-Protocol	MITT and Per-Protocol	Per-Protocol	

Aim 1 (non-inferiority of TM to SC):

- The primary analysis will be conducted on the **per-protocol** population.

- A supportive secondary analysis will be conducted on the **MITT** population.
- Sensitivity analyses of the primary analysis will add patients to the per-protocol population who were randomized to TM but who (A) were never treated (imputed as failures with time to failure = 6 months), or (b) were switched during surgery from TM to NTR (A1PPS population). Each sensitivity analysis will only be completed if the additional patients add up to at least 5 patients.

Aim 1a (If TM is found to be non-inferior to SC, then a step-down comparison will evaluate superiority of TM to SC):

- The primary analysis will be conducted on the **MITT** population.
- A supportive secondary analysis will be conducted on the **Per-Protocol** population.
- A sensitivity of the primary analysis will add patients to the MITT population who were randomized to SC or TM but who were never treated (imputed as failures with time to failure = 6 months). Sensitivity analysis will only be completed if the additional patients add up to at least 5 patients.

Aims 2 and 3 (superiority of SC to NTR and superiority of TM to NTR):

- The primary analysis will be conducted on the **MITT-narrow** population.
- A supportive secondary analysis will be conducted on the **Per-Protocol** population, and also on the **MITT** population.

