- A sensitivity of the primary analysis will add patients to the MITT-narrow population who were randomized to SC or TM but were never treated (imputed as failures with time to failure = 6 months). Sensitivity analysis will only be completed if the additional patients add up to at least 5 patients in either the SC or the TM treatment group.

All secondary efficacy evaluations will be analyzed on the **MITT** population (primary) and also on the **Per-Protocol** population (supportive).

Safety Evaluations:

- All safety analyses will be conducted on the safety population (with selected switchers presented as treated).

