#### Pelvic Floor Disorder

For a sensitivity analysis , to be conservative, we should assume they did not get surgery for a reason related to the type of surgery (Biased) and impute a worst outcome. This sensitivity analysis will only be done if there are at least 6 participants in this category in a treatment group.	Do a sensitivity analysis adding TM cases only to the primary PP analysis as failure at 6 months to test if TM is NI to SC cases – this stacks the deck in favor of SC.	Do a sensitivity analysis adding SC and TM cases only to the primary MITT analysis, as failures. This does not stack the deck in favor of either treatment group.	Do a sensitivity analysis adding SC and TM cases only to the primary MITT-narrow analysis, as failure at 6 months - this stacks the deck in favor of NTR (presumed to be the worst treatment)
Randomized but received AN AI	LTERNATE protocol treatment at	MD discretion (cases 4-6):	
4 . NTR switched to TM or SC This should never happen, as NTR should never be contra- indicated. Switching would be BIASED as other 2 treatments are expected to be superior	N/A (exclude from PP pop definition)	N/A (include in MITT definition)	INCLUDEThis is assumed to be conservative as switch is expected to improve outcome of NTR and thus make planned superiority comparison tougherSecondary Supportive analysis: EXCLUDE from a PP analysis
5. SC or TM switched to NTR	EXCLUDE	INCLUDE	INCLUDE
Although the protocol did not specify a plan of what to do if SC or TM could not be done, including switchers in the ITT defines the primary hypothesis to compare "start out planning	Major protocol violation, it is assumed this would make the outcome worse for the switcher and muddy the comparison.	This is intent-to-treat, or ICH E9R1 "treatment policy" and compares the treatments as they were planned to be.	This is assumed to be conservative as switch is expected to worsen outcome of SC/TM and thus make planned superiority comparison tougher.

Pelvic Floor Disorder

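### The SAP's MITT definition drops the protocol's unrelated-reason condition, so allocation-related non-treatment is left out of the primary and supportive superiority analyses and returns only in a conditional SC/TVM sensitivity analysis

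*SAP*

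**What the plan says.** **Protocol.** Section M.2 starts from intent-to-treat and removes women who "never received surgery due to patient-specific reasons unrelated to the randomized treatment". Sections H.1 and N.5 attach the same condition to discontinuing women who are not scheduled for surgery within 6 months. Appendix B, section 6, is different: it describes the main study's analysis as limited to randomised and treated women, with no test of reason.

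**SAP.** Section 5 says the intent-to-treat population "is modified to remove patients who were randomized but never received surgery". The formal MITT definition is "all randomized patients, excluding patients who discontinued the study without having surgery". Neither mentions the reason, although SAP 7.8 keeps the unrelated-reason condition for the 6-month discontinuation rule. Neither the protocol history (SAP 1) nor the list of updates (SAP 12) records the difference.

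**Where it applies.** MITT is primary for Aim 1a. For the two mesh-versus-NT comparisons, "The primary analysis will be conducted on the MITT-narrow population", and MITT-narrow is a subset of MITT. The supportive populations are MITT and per-protocol, which exclude the same women.

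**The planned check.** Sensitivity analyses add back women "randomized to SC or TM but were never treated (imputed as failures with time to failure = 6 months" for the NT comparisons, and likewise for Aim 1a. SAP Table 3 (definition of analysis populations) gives the reason: "we should assume they did not get surgery for a reason related to the type of surgery (Biased) and impute a worst outcome".

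**The concern.** Removing a woman after randomisation is harmless to a superiority comparison only if the reason has nothing to do with her arm. The protocol's condition draws that line and the SAP's definition erases it.

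Arm-related non-treatment is possible here. Randomisation comes before scheduling. Surgeons and coordinators know the allocation (masking tables in Protocol H.2 and SAP 4.4.1). Protocol H.1 notes that robotic rooms are in heavy demand, so delay may differ by arm. Protocol N.1 records strong views against mesh among some physicians and patients. The SAP itself treats non-surgery as possibly arm-related when it justifies the sensitivity analysis, yet leaves such women out of the primary set.

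At stake is a shift in the estimated mesh advantage. If the omitted women are mostly in a mesh arm, omission flatters mesh.

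**Working it through.** **1. The definitions compared.**

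| Woman randomised, no surgery | Protocol M.2 | Protocol App. B | SAP MITT |
|---|---|---|---|
| Reason unrelated to allocation | removed | removed | removed |
| Reason related to allocation | kept | removed | removed |

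Only the second row is in dispute.

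**2. The trigger for the add-back analysis.** The aim-by-aim bullets in SAP 5 require at least 5 women (in total for Aim 1a; in either the SC or the TVM arm for Aims 2 and 3). The general rule in SAP 5 and SAP Table 3 require at least 6. Population sizes are evaluated after database lock and unblinding, though before any efficacy analysis. With exactly 5 cases, the conflict would be settled by people who know the arms. With 4 in one mesh arm and none in the other, no version fires.

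**3. The plan's own figures** (Protocol M.1, SAP 6). Inputs: 2-year success of 80% and 60%, 2-year accrual plus 3 years, 5% loss per year, 121 per arm.

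- Hazards: −ln(0.8)/2 = 0.1116 and −ln(0.6)/2 = 0.2554. NT:mesh ratio = 2.29.
- Margin: −ln(0.65)/2 = 0.2154, and 0.2154/0.1116 = 1.93.
- Event probability over planned follow-up: 0.326 (mesh), 0.585 (NT).
- Schoenfeld formula, one-sided 0.03, 85% power: 79 events, and 79/(2 × 0.326) ≈ 121 per arm. Superiority power at two-sided 0.01 is 94.3% to 96.2% depending on formula, against the stated figure of more than 93%.

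The design figures reproduce. They do not depend on the MITT wording, because the target is 363 randomised and treated women.

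**4. Effect on the hazard ratio.** The number k of allocation-related untreated women is an assumption. Each counts as one failure with 0.5 years of follow-up, as in the SAP's imputation.

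- Mesh arm without them: 121 × 0.3264 = 39.5 events over 39.5/0.1116 ≈ 353.9 woman-years.
- NT arm: 121 × 0.5847 = 70.8 events over 70.8/0.2554 ≈ 277.0 woman-years.
- Mesh rate with k added: (39.5 + k)/(353.9 + 0.5k). The NT rate is formed the same way.

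| k in mesh | k in NT | Mesh rate | NT rate | NT:mesh HR |
|---|---|---|---|---|
| 0 | 0 | 0.1116 | 0.2554 | 2.29 |
| 3 | 0 | 0.1195 | 0.2554 | 2.14 |
| 4 | 0 | 0.1222 | 0.2554 | 2.09 |
| 6 | 0 | 0.1274 | 0.2554 | 2.00 |
| 3 | 3 | 0.1195 | 0.2648 | 2.22 |
| 6 | 6 | 0.1274 | 0.2741 | 2.15 |
| 0 | 6 | 0.1116 | 0.2741 | 2.46 |

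**5. Effect on power.** A simulation of exponential rate ratios (3,000 runs, two-sided 0.01) gives 95.2% with k = 0, 90.7% with 4 and 87.9% with 6 in one mesh arm only. With 6 in each arm it gives 94.5%.

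**The case against.** **The protocol is not uniform.** Appendix B matches the SAP rule, and the enrolment target is framed as randomised and treated women. This stands: M.2, Appendix B and the SAP must be reconciled. M.2 is, however, the section that defines the populations.

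**The SAP already has a check.** A reader might infer that allocation-driven non-treatment vanishes from the superiority analyses altogether. The documents do not support that. The add-back covers every untreated SC and TVM woman regardless of reason, which is harsher on mesh than the protocol's rule. What remains is that it depends on an inconsistent trigger and, because it ignores reason, does not rebuild the protocol's MITT.

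**Leaving out NT women is deliberate.** SAP Table 3 explains that this favours NT, the conservative direction for Aims 2 and 3. This stands: adding 6 NT failures alone would raise the ratio to 2.46. The omission of NT women is not a defect in that bound.

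**The main routes are narrow.** Participants are masked until after surgery. SAP 5 describes switching to another study procedure when the allocated one is contraindicated, and switchers stay in MITT as randomised. Pending TVM women were re-randomised. All this limits the likely number but does not make it zero.

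**There is no outcome to analyse.** SAP Table 3 describes these women as having no follow-up, and failure time runs from surgery. M.2 gives no imputation rule. Retaining them therefore means moving a worst-case imputation into the primary analysis, which is a judgement and should be stated as one.

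**Conclusion.** The discrepancy is real, undeclared, and touches the primary population for all three superiority aims. Its size cannot be known from the documents. If 3 to 6 allocation-related untreated women fell in one mesh arm only, the NT:mesh ratio would be about 2.14 to 2.00 instead of 2.29; with equal numbers in the NT arm it would be 2.22 to 2.15. These figures assume the design hazards, the planned follow-up and failure at 6 months for every such woman.

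A reader might work from 2-year proportions and get a larger drop: ln(0.6)/ln(1 − 27.2/124) = 2.06 for 3 women and ln(0.6)/ln(1 − 30.2/127) = 1.88 for 6. That overstates the effect, because the primary model uses 36 to 60 months of follow-up. Nor do the documents show that any superiority conclusion would be overturned: with 4 women in one mesh arm, below either trigger, simulated power is still 90.7%. The change is worth making because it is cheap and removes an avoidable source of bias.

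**What to change.** **Preferred.** Restore the protocol's unrelated-reason condition in the SAP's MITT and MITT-narrow definitions, and bring Protocol Appendix B, section 6, into line. Classify each reason for no surgery masked to arm, within the review of withdrawal reasons already planned in SAP 7.5. Keep allocation-related cases in the analysis, using the existing imputation of failure at 6 months.

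**Minimum.** Declare and justify the departure from Protocol M.2. Run the add-back sensitivity analysis whatever the count, which also removes the conflict between 5 and 6 and the post-unblinding check for this analysis. Keep the SC/TVM-only version as the conservative bound for the comparisons with NT, and add an all-arms version beside it.

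**Cost.** SAP wording, a short masked review, one extra model run, and possibly a slightly less favourable superiority estimate.
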